4.2.2 NUMBER OF PARTICIPANTS

Up to 50 participants will be screened using CORE records and advertising approved by the UW Office of Research Ethics. Up to 50 participants will be dispensed/randomized with study products, with a target of at least 10 symptomatic and 10 asymptomatic participants completing the study. Informed consent will be obtained for all participants prior to their enrolment in the study.

4.2.3 INCLUSION AND EXCLUSION CRITERIA

A person is eligible for inclusion in the study if he/she:

1. Is at least 17 years of age and has full legal capacity to volunteer;
2. Has read and signed an information consent letter;
3. Is willing and able to follow instructions and maintain the appointment schedule;
4. Has worn soft contact lenses for a minimum of 6 months;
5. Currently wears soft contact lenses for at least 4 days per week and 8 hours per day;
6. Has an acceptable fit and comfort with both study contact lenses in the powers available;
7. Has ≤ 1.00 DS difference between eyes in their habitual contact lenses;

8. Is willing to be awake for at least 2 hours before visit 2;
9. Is willing to not wear eye makeup on the day of visit 2 and 3;
10. Is willing to not use eye drops or artificial tears on the day of visits 1, 2, and 3;
11. Has a wearable pair of spectacles.

A person will be excluded from the study if he/she:

1. Is participating in any concurrent clinical or research study;
2. Has any known active* ocular disease and/or infection;
3. Has a systemic condition that in the opinion of the investigator may affect a study outcome variable;
4. Is using any systemic or topical medications that in the opinion of the investigator may affect a study outcome variable;
5. Has known sensitivity to sodium fluorescein dye;
6. Is pregnant, lactating or planning a pregnancy at the time of enrolment (by verbal confirmation at the screening visit);
7. Is aphakic;
8. Has undergone refractive error surgery;
9. Has a known sensitivity to petroleum jelly (Vaseline);
10. Has epilepsy and/or a sensitivity to flashing lights;
11. Wears toric contact lenses;
12. Has any physical impairment that would interfere with holding the evaporimeter;
13. Has taken part in another research study within the last 14 days.

* For the purposes of this study, active ocular disease is defined as infection or inflammation which requires therapeutic treatment. Mild (i.e. not considered clinically relevant) lid abnormalities (blepharitis, meibomian gland dysfunction, papillae), corneal and conjunctival staining and dry eye are not considered active ocular disease. Neovascularization and corneal scars are the result of previous hypoxia, infection or inflammation and are therefore not active.

4.2.4 REPEATED SCREENINGS

In some circumstances a repeated screening may need to be scheduled. Examples include, but are not limited to:

1. Incomplete information available at time of screening to determine eligibility (e.g. current lens brands worn, history from current eye care practitioner etc.)
2. Study procedures unable to be completed in time scheduled for visit;

3. Study products not available at the time of the screening visit;
4. A transient health condition which may affect the eye(s) (e.g. a common cold, active allergies, fatigue etc;)
5. The short term use of medications (e.g. antibiotics, antihistamines etc.)
6. Reassessment of baseline ocular conditions (e.g. corneal and/or conjunctival staining, scars etc.)

The maximum total number of screenings permitted will be 3 (i.e. 2 repeated screenings are allowed).

4.3 STUDY MATERIALS

4.3.1 LENSES

Details of the study lenses are shown in Table 1.

Table 1: Lens parameters to be used in this study

| Lens | Biotrue ONEday | DAILIES TOTAL1 |
|------------------|------------------------------------------------------------------------------------------------------|----------------------------------------------------------------------------------------------------|
| Manufacturer | Bausch & Lomb Inc. | Alcon Canada Inc. |
| Material | nesofilcon A | delefilcon A |
| HC licence # | 89630 | 87774 |
| EWC (%) | 78% | core 33%, surface ≥ 80% |
| Dk/t at -3.00D | 42 | 156 |
| Sphere power (D) | +0.50 to +6.00 (in 0.25 steps) -0.50 to -6.00 (in 0.25 steps) -6.50 to -9.00 D (in 0.50 steps) | +0.50 to +6.00 (in 0.25 steps) -0.50 to -6.00 (in 0.25 steps) -6.50 to -9.00 (in 0.50 steps) |
| Base curve (mm) | 8.6 | 8.5 |
| Diameter | 14.2 | 14.1 |

4.3.2 LENS CARE SYSTEM

No contact lens care system is required for this study as all the lenses are daily disposable lenses designed to be worn for a single day and then discarded.

Lenses will be discarded after being worn at the screening visit (Visit 1) and at the end of the follow up visit (Visit 3).

4.3.3 REWETTING DROPS & SALINE

Participants will not be encouraged to use rewetting drops; however, those who habitually use rewetting drops will be allowed to continue using their normal drops, except for on the day of the screening (Visit 1) and on the day of Visits 2 and 3. Rewetting drop use will be recorded at each visit. In the event of an adverse event, rewetting drops may be given to participants.

Saline solution may be used to rinse residual sodium fluorescein from the eyes following corneal staining assessment.

The use of saline for rinsing the CL prior to insertion is permitted, if necessary. If initial CL discomfort is reported after a lens has been inserted, a CL may be removed, rinsed with saline, and re-inserted.

4.3.4 ORDERING CONSUMABLES

Study products will be obtained through commercial sources.

4.3.5 DISPOSING OF CONSUMABLES

Lenses worn at the scheduled visits will be collected from the participants and disposed of according to UW guidelines.

4.3.6 PRODUCT ACCOUNTABILITY

Accountability logs will be kept to include the number of lenses dispensed. All products dispensed to participants will be recorded in the study binder.

4.3.7 CONTACT LENS DISPENSING

At Visit 1, participants will insert the CLs directly from the labelled blister pack in order to ensure an acceptable lens fit.

At Visit 2, the CLs will be provided to the participant after being transferred, complete with the blister pack solution, to a CL cup; in order to maintain participant and investigator masking.

The use of saline for rinsing the CL prior to insertion or just after insertion is permitted, if necessary. Saline will not be dispensed during the study.

4.4 SCHEDULED AND UNSCHEDULED VISITS

This study has a total of 3 study visits, including the screening visit, including:

- Visit 1: Screening and fitting of study lenses,
- Visit 2: Baseline measurements and dispensing of study lenses,
- Visit 3: Follow-up visit with study lenses on the same day as Visit 2 and study exit.

4.4.1 STUDY VISITS

The study has a total of 3 study visits, including the screening visit. Visit 2 and Visit 3 will occur on the same day and will be scheduled up to 14 days after the screening visit (Visit 1). The total time

commitment for the scheduled visits is 4 hours of active participation. The summary of visit codes is shown in Table 2.

Table 2: Summary of visit codes

| Visit # | Visit code | Study Day | Visits | Duration (hours) |
|---------|------------------------------------|-----------|--------------------------------------------------------------------------------------------------------------------------|------------------|
| 1 | V1 (V1-R1, V1-R2 for re-screening) | 1 | Screening and fitting | 1.5 |
| 2 | 2 | 2 | Baseline & dispense study lenses Vst 2 will be scheduled up to 14 days after Vst 1 | 1.5 |
| 3 | 3 | 2 | Follow up with study lenses & study exit Vst 3 will be scheduled 5.5 hours ± 30 minutes after the completion of Vst 2 | 1 |

4.4.2 VISIT 1: SCREENING

All participants who sign the informed consent letter will be assigned a study ID number. The investigator will determine participant eligibility using the inclusion and exclusion criteria. Ineligible participants will be discontinued from the study. The procedures to be performed are outlined below:

- Participants will attend the screening visit having not worn their habitual contact lenses on the day of the visit.
- Participants will attend the screening visit having not used any eye drops or artificial tears on the day of the visit.
- The participant will be required to read and sign an Informed Consent Form prior to enrollment. When the participant has signed the consent form, the participant will be considered to be enrolled in the study.
- Participant demographics and medical history (age, sex, medical conditions, medications, allergies)
- Contact lens history (own lens information and wearing time)
- Contact lens dry eye questionnaire-8 (CLDEQ-8)
- Monocular and binocular logMAR visual acuity will be recorded with high contrast letters under high illumination with spectacles or spectacle refraction.
- Assessment of meibomian gland expression
- Lid margin assessment
- Slit lamp biomicroscopy
- The investigator will confirm that the participant meets the eligibility specifications set out in the inclusion criteria and exclusion criteria and is eligible to continue with the remainder of the screening visit.

- Trial fitting of both study lenses will be done:
 - The lenses will be inserted by the participant directly from the blister pack based on their current contact lens power.
 - The contact lenses will be allowed to settle for 10 minutes.
 - Monocular and binocular logMAR visual acuity will be recorded with high contrast letters under high illumination with the study lenses.
 - Spherical over-refraction
 - Monocular and binocular logMAR visual acuity will be recorded with high contrast letters under high illumination with the study lenses and over-refraction.
 - Contact lens fit will be assessed.
- Anterior eye photographs of each eye will be taken with a slit lamp camera.
- Participants will practice evaporimetry measurements.
- Removal of study lenses.
- Measurement of volume within the goggle.
- Slit lamp biomicroscopy (safety check)
- Monocular and binocular logMAR visual acuity will be recorded with high contrast letters under high illumination with spectacles or spectacle refraction.
- The investigator will confirm that the participant meets the eligibility specifications set out in the inclusion criteria and exclusion criteria and is eligible to continue with the study.

4.4.3 VISIT 2: BASELINE AND DISPENSING VISIT

- Participants will attend the visit having been awake for at least 2 hours.
- Participants will not have worn any contact lenses, used any eye drops or artificial tears, or worn any eye makeup on the day of the visit. Participants who have worn lenses, used eye drops, used artificial tears, or worn eye makeup on the day of the visit will be rescheduled.
- Monocular and binocular logMAR visual acuity will be recorded with high contrast letters under high illumination with spectacles or spectacle refraction.
- Slit lamp biomicroscopy using white light.

The participant will be assigned a randomization ID in order to determine which type of CL will be inserted into each eye.

Participants will be required to adapt to the room environment for at least 15 minutes prior to reporting subjective monocular ratings and performing baseline evaporimetry measurements. The

participant will apply thin layer of petroleum jelly will be applied to the skin surrounding the eye using a cotton tipped applicator to minimize the amount of evaporation from the skin.

- The participant will be asked to give subjective monocular ratings for:
 - Comfort
 - Dryness
 - Burning or stinging
- Baseline evaporimetry measurements without contact lenses
- Non-invasive pre-ocular tear film break up time (Tearscope)
- Lipid layer thickness (Tearscope)
- Lipid layer thickness (LipiView II)
- Evaporimetry measurements will be repeated at least 15 minutes after the initial baseline measurement.
- Non-invasive pre-ocular tear film break up time (Tearscope)
- Lipid layer thickness (Tearscope)
- Lipid layer thickness (LipiView II)
- The participant will wipe away petroleum jelly from skin surrounding the ocular surface using a tissue.
- Contact lenses will be given to the participants in a masked manner (Section 4.3.7).
- The study contact lenses will be inserted by the participant.
- The lenses will be allowed to settle for at least 15 minutes.
- The participant will apply a thin layer of petroleum jelly will be applied to the skin surrounding the eye using a cotton tipped applicator to minimize the amount of evaporation from the skin.
- The participant will be asked to give subjective monocular ratings for:
 - Comfort
 - Dryness
 - Burning or stinging
- Baseline evaporimetry measurements with contact lenses.
- Non-invasive pre-lens tear film break up time (Tearscope)
- Lipid layer thickness (Tearscope)
- Lipid layer thickness (LipiView II)
- Contact lens fit will be assessed.

- Monocular and binocular logMAR visual acuity will be recorded with high contrast letters under high illumination with contact lenses.
- The participant will wipe away petroleum jelly from surrounding the ocular surface using a tissue.

Participants will continue to wear the study lenses and will be advised not to use any eye drops or eye makeup. Participants will be instructed to return to CORE in 5.5 hours \pm 30 minutes for their next visit.

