4.4.4 VISIT 3: FOLLOW UP & STUDY EXIT

Participants will attend the visit having not used any eye drops or eye makeup on the day of the visit.

- Monocular and binocular logMAR visual acuity will be recorded with high contrast letters under high illumination.
- Contact lens fit will be assessed.

Participants will be required to adapt to the room environment for at least 15 minutes prior to reporting subjective monocular ratings and performing evaporimetry measurements. The participant will apply thin layer of petroleum jelly will be applied to the skin surrounding the eye using a cotton tipped applicator to minimize the amount of evaporation from the skin.

- The participant will be asked to give subjective monocular ratings for:
 - Comfort
 - Dryness
 - Burning or stinging
- Evaporimetry measurements with contact lenses. Evaporimetry measurements will not be taken until the study lenses have been worn for a minimum of 6 hours.
- Non-invasive pre-lens tear film break up time (Tearscope)
- Lipid layer thickness (Tearscope)
- Lipid layer thickness (LipiView II)
- The participant will wipe away petroleum jelly from the skin surrounding the ocular surface using a tissue.
- Contact lens removal.
- Slit lamp biomicroscopy.
- Exit monocular and binocular logMAR visual acuity will be recorded with high contrast letters under high illumination with spectacles or spectacle refraction.

Study Exit

- The study exit form will be completed when a participant exits the study. This will occur either at study completion, or if the participant is discontinued from the study at another time. A study exit form must be completed for all participants who have been given a study number. If in the opinion of the investigator post-study follow-up visits are required, the exit form will be completed after the last follow-up visit.
- The participant will be discharged and will sign the study completion forms and receive remuneration for participating in the study.

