4.5.15 SUBJECTIVE COMFORT RATINGS

Participants will be asked to fill a numerical analog scale for comfort, dryness, and burning or stinging for each eye on a 0-100 scale:

- At Visit 2, before & 15 minutes after lens insertion
- At Visit 3, after at least 6 hours of contact lens wear.

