6 POTENTIAL RISKS AND BENEFITS TO HUMAN PARTICIPANTS

This is a minimal risk study because of the use of marketed products and standard optometric assessments with two investigational, non-invasive devices (the prototype evaporimeter and the modified swimming goggles used to measure volume).

Contact lenses in this study will be worn on a daily wear basis, for approximately 6 to 7 hours. Adverse events and/or complications in daily wear of soft contact lenses can occur (eg: inflammation and infection). When contact lenses are worn on a daily wear basis there is a small risk of an adverse event compared to not wearing contact lenses. When contact lenses are worn on an extended wear basis, there is a significantly increased risk of an adverse reaction compared with wearing contact lenses on a daily wear basis.

Additionally, it is possible that participants may experience temporary discomfort associated with the study procedures (saline)/products/devices including: burning and stinging, blurred vision, sandiness or grittiness, light sensitivity, dryness, itching, crusty eyes and foreign body sensation.

A dye (fluorescein) normally used for eye exams is being used in this study. Although rare, it is possible that participants may have an allergic reaction to the dye. This could cause discomfort to their eye.

Routine clinical procedures including visual acuity, anterior ocular health assessment, and contact lens fitting will be used.

One clinical procedure (evaporimetry) will be conducted with an investigational device consisting of a pair of modified swimming goggles containing a temperature and humidity sensor embedded in each lens of the goggle. This procedure poses minimal risk to the participants as the device does not touch the eye and the portion of the goggle which will come in contact with the skin surrounding the eye will be cleaned with alcohol wipes between each use. Participants may experience temporary discomfort associated with petroleum jelly including; burning, stinging, irritation, blurred vision, and foreign body sensation.

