10 STATISTICAL ANALYSIS AND DATA MANAGEMENT

10.1 STATISTICAL ANALYSIS

All data will be analyzed by CORE at the University of Waterloo on unmasked data using Microsoft Excel and statistical analysis software such as GraphPad and SPSS. Interim data analysis will be conducted after 10 symptomatic and 10 asymptomatic participants have completed the study to determine the optimal time period over which to calculate the slope. The results of the interim data analysis will also be used to calculate the sample size.

Descriptive statistics will be provided on information regarding baseline variables (age, sex, contact lens refractive error distribution, etc.). Data may be evaluated for individual groups

(asymptomatic versus symptomatic) and when both groups are combined. Data will be tested for normality of distribution using Shapiro-Wilk tests. A p -value of < 0.05 will be considered statistically significant. Additional analysis may be conducted.

Table 4 lists the primary outcome variables and anticipated statistical procedures.

Table 4: Outcome variables and anticipated statistical procedures

| Variable | Analysis | Statistical test |
|--------------------------------------------------------------------------------------------------------------------------------------------------------------|--------------------------------------------------------------------------------------------------------------------|--------------------------------------------------------------------------------------------------------------------|
| Tear evaporation rate | Change in relative humidity over time | Slope |
| Tear evaporation rate/Time | Effect of lens type | RMANOVA Mauchly's test of sphericity Greenhouse-Geisser p values Tukey HSD post hoc Paired t -test |
| Tear evaporation rate/ Subjective ratings/Non- invasive breakup time/Lp d ayer thickness (Lp View II - continuous)/Area of the ocular surface | Relationship between tear evaporation rate and subjective comfort and dryness/other tear film assessments | Pearson correlation – r |
| Tear evaporation rate/ Lp d ayer thickness (Tearscope - ordinal)/ Volume of the goggle | Relationship between tear evaporation rate and lpdayer thickness | Spearman correlation – ρ |

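### Comfort, dryness and burning/stinging are rated with petroleum jelly already around the eyes, which can add avoidable noise; rating before the jelly costs nothing

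*Combined protocol and SAP*

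**What the plan says.** Section 4.4.3 has two rating points at Visit 2, one before lens insertion and one after settling. Section 4.4.4 has one at Visit 3. In all three the text runs in the same order: adapt or settle, apply jelly, rate, then evaporimetry. At the with-lens point of Visit 2 the steps are consecutive bullets: "The participant will apply a thin layer of petroleum jelly will be applied to the skin surrounding the eye", then "The participant will be asked to give subjective monocular ratings for" comfort, dryness, and burning or stinging. At the no-lens point and at Visit 3 the jelly step closes the paragraph above the bullets; for Visit 3 it reads "The participant will apply thin layer of petroleum jelly will be applied to the skin surrounding the eye".

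The only purpose given for the jelly is "to minimize the amount of evaporation from the skin". Section 6 says of it: "Participants may experience temporary discomfort associated with petroleum jelly including; burning, stinging, irritation, blurred vision, and foreign body sensation".

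Section 4.5.15 defines the scale: "Participants will be asked to fill a numerical analog scale for comfort, dryness, and burning or stinging for each eye on a 0-100 scale". It times the ratings by lens insertion or wear ("At Visit 2, before & 15 minutes after lens insertion", and after at least 6 hours of wear at Visit 3) and does not mention the jelly. Section 2 lists comfort and dryness among the other variables of interest. Table 4 in section 10.1 plans Pearson correlations for the "Relationship between tear evaporation rate and subjective comfort and dryness/other tear film assessments".

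**The concern.** One of the three rated items, burning or stinging, is also a listed effect of the jelly. Irritation and foreign body sensation bear on comfort. A participant who feels the jelly cannot be told apart from one who feels the lens or has dry-eye symptoms, because every rating is made with a fresh layer on the skin and the plan has no rating without one. What is at stake is the quality of secondary variables: their absolute levels, and the strength of the correlations between ratings and evaporation. The ratings do not need the jelly, so this noise is avoidable.

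**Working it through.** **1. Order of steps.** The documents give no effect size, SD or correlation for the ratings, so there is no planned figure to reproduce. The point rests on comparing sections.

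- 4.4.3 (both rating points) and 4.4.4: jelly is listed before the ratings, and evaporimetry after them. No interval is stated.
- Table 3: the subjective-assessment row stands above the jelly row. This does not settle the order, because the table also lists lens removal above evaporimetry, whereas 4.4.4 removes the lenses afterwards.
- 4.5.15: silent on the jelly.

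**2. Overlap of rated items with the section 6 list.**

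- Burning/stinging: direct. It is collected, but it is not in the section 2 list and is not named in the analysis column of Table 4.
- Comfort: direct, through irritation and foreign body sensation.
- Dryness: not a listed jelly effect, so any link is indirect.

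**3. What cancels.** Write rating = symptom + jelly effect.

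- Equal effect in both eyes: it drops out of the difference between DAILIES TOTAL1 and Biotrue ONEday.
- Same effect at every rating: it drops out of change from the no-lens baseline.
- Fully eye-specific effect: the mean difference stays unbiased, but its SD is multiplied by √(1 + k²), where k = SD(jelly effect) / SD(symptom) and the eyes are taken as independent. For k = 0.5 this is √1.25 = 1.118; for k = 1 it is √2 = 1.414.

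**4. Correlation with evaporation (assumed inputs).** If the jelly effect is independent of symptom and evaporation, r_obs = r_true / √(1 + k²). Power uses Fisher's z: Φ(atanh(r_obs)·√(n − 3) − 1.96), taking the protocol's 0.05 as two-sided (sidedness is not stated). The values n = 20 and n = 50 are the completer target (10 + 10) and the maximum randomized in section 4.2.2.

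| r_true | k | r_obs | Power, n = 20 | Power, n = 50 | n for 80% power |
|---|---|---|---|---|---|
| 0.5 | 0 | 0.500 | 62% | 97% | 30 |
| 0.5 | 0.25 | 0.485 | 59% | 95% | 31 |
| 0.5 | 0.5 | 0.447 | 51% | 91% | 37 |
| 0.5 | 1 | 0.354 | 33% | 72% | 61 |
| 0.3 | 0 | 0.300 | 25% | 56% | 85 |
| 0.3 | 0.5 | 0.268 | 20% | 47% | 107 |
| 0.3 | 1 | 0.212 | 14% | 31% | 173 |

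**5. Which k is plausible?** Suppose a share p of participants feels the jelly and loses d points, with p from 10% to 30% and d from 10 to 20 (assumed).

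- The mean shift is p·d, from 0.10 × 10 = 1 to 0.30 × 20 = 6 points.
- The SD of the effect is d·√(p(1 − p)), from 10 × √0.09 = 3.0 to 20 × √0.21 = 9.2 points.
- With a symptom SD of 15 to 25 points (also assumed), k runs from 3.0/25 = 0.12 to 9.2/15 = 0.61.
- A true r of 0.50 then becomes 0.50/√1.0144 = 0.496 at the low end and 0.50/√1.373 = 0.427 at the high end.

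The mean shift moves absolute levels only. A Pearson correlation is unchanged by adding a constant; only the added variance weakens it.

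**The case against.** The other side has several good arguments.

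- *Secondary use only.* The hypotheses in section 3 all concern evaporation, and Table 4 uses the ratings only in exploratory correlations within a pilot that has no powered sample size. This stands, and it keeps the priority low.
- *Safeguards exist.* Known sensitivity to petroleum jelly is an exclusion, the layer is thin and on skin, and 4.5.14 asks for care in removal. These reduce the risk but do not remove it: only known sensitivity is excluded, and section 6 still gives the warning for those enrolled.
- *The risk wording is precautionary.* It says the effects may occur, and section 6 lists the same symptoms for saline. This is fair: it shows that an effect is possible, not how large it is.
- *Table 3 lists ratings first.* Its row order is not chronological, so it cannot override the scripts. It does show that the order should be stated once.

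Stronger readings are also tempting, and the documents do not support them. A reader might infer that the no-lens versus with-lens comparison is biased because it sets one application against two. But the first layer is wiped off and at least 15 minutes of settling follow, so each rating is made under one fresh layer; a carry-over effect is conjecture. A reader might also infer that symptomatic wearers react more to the jelly; nothing in the documents says so. Neither comparison is a specified test of the ratings. Section 10.1 says only that data may be evaluated by group.

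**Conclusion.** The point holds as a free improvement to secondary measurements. The scripts put the jelly before every rating, the ratings do not need it, and its listed effects overlap with the comfort and burning/stinging items. The consequences are possible noise, shifted absolute levels and weaker correlations between ratings and evaporation. The size is unknown; under the assumptions shown, a true correlation of 0.50 would be observed at about 0.43 to 0.50. These figures assume a jelly effect independent of symptom and evaporation.

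It would go too far to conclude that the between-lens comparison or the change from baseline is biased: a symmetric effect cancels in the first and a constant effect in the second. It would also be wrong to read this as a threat to the primary outcome. The humidity slope does not depend on when the ratings are taken.

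**What to change.** In 4.4.3 (both rating points) and 4.4.4, move the comfort, dryness and burning/stinging ratings to the end of the existing adaptation or settling period, before the jelly step. Then apply the jelly and start evaporimetry as now. Keep the timing in 4.5.15: 15 minutes after insertion at Visit 2, and at least 6 hours of wear at Visit 3. State the order in 4.5.15 and arrange the rows of Table 3 to match.

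The cost is a change of order in the visit scripts, with no added time, staff or procedure. The first no-lens rating becomes fully jelly-free. The later two are made without a fresh layer, although residue from an earlier, wiped-off application could remain. If the order is kept as it is, report it as a limitation and interpret the ratings mainly through within-participant contrasts.
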